11.8 End of trial participation

Participants will continue the normal standard of care after participating in the trial. A participant is deemed to have completed the trial once they have completed their 12-month follow up assessment.

11.9 Trial restrictions

There are no trial-related restrictions in addition to standard care. Regardless of the trial arm the participant is assigned to and the trial medications being/not being taken, the treating clinician will assess the participant regularly and will decide on the clinical course for the patient as part of routine standard care. This may involve withholding PTP if deemed clinically necessary.

12. Assessment of safety

This trial is a Type A study (low risk), as all the IMPs being used are licensed medications and the dose and frequency of administration of these IMPs will be as per routine clinical care (with only the time-point of administration being varied). Therefore, safety assessments are not of primary concern (unless they are SARs or SUSARs).

Principal investigators are required to report to the central coordinating team only selected AEs or ARs and if any AE or ARs fulfil the criteria for a SAR or SUSAR.

12.1 Definitions

12.1.1 Adverse event (AE)

Any untoward medical occurrence in a participant or clinical trial participant administered a medicinal product which does not necessarily have a causal relationship with this treatment. An adverse event can therefore be any unfavourable and unintended sign (including an abnormal laboratory finding), symptom, or disease temporally associated with using an investigational medicinal product, whether considered related to the investigational medicinal product.

Recording of adverse events must start from the point of Informed Consent regardless of whether a participant has yet received a medicinal product.

The safety profiles of all drugs used for VTE prophylaxis are well established, and due to the pathology of TBI, trial participants will be regularly monitored and assessed in the intensive care environment at regular intervals throughout the trial, over and above routine clinical care. Given the pragmatic nature of the trial and that the potential risk associated with the trial drug is 'no higher than standard care',

only AEs of special interest (AESI) will be recorded on CRF and sent to the coordination centre as listed below.

Adverse events of special interest (AESI) – assessed and reported in accordance with criteria published by the International Society of Thrombosis and Haemostasis. – see Appendix 1.

The following should all be recorded on the AESI form in the eCRF.

- Thrombocytopenia
- Thrombocytosis
- Prosthetic cardiac valve thrombosis
- Cutaneous vasculitis
- Eosinophilia
- Skin reactions
- Angioedema
- Priapism
- Stevens-Johnson syndrome
- Acute generalised exanthematous pustulosis (AGEP)

12.1.2 Adverse reaction to an investigational medicinal product (AR)

All untoward and unintended responses to an investigational medicinal product related to any dose administered. All adverse events judged by either the reporting investigator or the sponsor as having a reasonable causal relationship to a medicinal product qualify as adverse reactions. The expression reasonable causal relationship means to convey in general that there is evidence or argument to suggest a causal relationship.

12.1.3 Unexpected adverse reaction

An adverse reaction, the nature or severity of which is not consistent with the applicable reference safety information (RSI). When the outcome of the adverse reaction is not consistent with the applicable RSI, this adverse reaction should be considered unexpected. The term “severe” is often used to describe the intensity (severity) of a specific event. This is not the same as “serious,” which is based on participant /event outcome or action criteria.

12.1.4 Serious Adverse Event or Serious Adverse Reaction (SAE / SAR)

Any untoward medical occurrence at any dose:

- results in death
- is life-threatening
- requires re-hospitalization or prolongation of existing inpatients’ hospitalisation, where it is not considered to be due to the initial trauma
- results in persistent or significant disability or incapacity
- is a congenital anomaly or birth defect
- is an important medical event - Some medical events may jeopardise the participant or may require an intervention to prevent one of the above characteristics/ consequences. Such events (hereinafter referred to as ‘important medical events’) should also be considered ‘serious’

Life-threatening in the definition of a serious adverse event or serious adverse reaction refers to an event in which the participant was at risk of death at the time of the event; it does not refer to

an event which hypothetically might have caused death if it were more severe.

12.1.5 Suspected Unexpected Serious Adverse Reaction (SUSAR)

A serious adverse reaction, the nature and severity of which is not consistent with the information set out in the Reference Safety Information.

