12.1.6 Reference Safety Information (RSI)

A list of medical events that define which reactions are expected for the IMP within a given trial and thus determines which Serious Adverse Reactions (SARs) require expedited reporting.

For this trial, the Reference Safety Information contains a clearly identified section 4.8 of the Summary of Product Characteristics (SmPC) for different drug classes.

12.1.7 Table for IMP class with SmPCs and text revision date for RSI/IMP class	RSI	Text revision Date
LMWH	Inhixa 4,000 IU (40 mg)/0.4 mL solution for injection	23/05/2023
Low molecular weight sulphated glycosaminoglyuronans	Danaparoid Sodium 750 anti-Xa units/0.6 ml, solution for injection	01/2021
Direct oral Anticoagulants (DOAC)	Pradaxa 150 mg hard capsules	12/04/2024
Synthetic pentasaccharide	Arixtra Fondaparinux sodium solution for injection 2.5 mg/0.5 ml	05/12/2023
Heparin	Heparin (Mucous) Injection BP 5,000 IU	28/09/2018

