12.6 Reporting of Suspected Unexpected Serious Adverse Reactions (SUSARs)

All suspected adverse reactions related to an investigational medicinal product (the tested IMP and comparators) which occur in the concerned trial and that are both unexpected and serious (SUSARs) are subject to expedited reporting. Please see section 4.8 for the Reference Safety Information for this trial.

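### Section 12.1.5 defines a SUSAR by nature and severity together, which is narrower than the unexpected-reaction definition in 12.1.3 (nature, severity or outcome) and the reporting rule in 12.6

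*Protocol*

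**What the plan says.** Four places in section 12 of the protocol bear on what counts as a SUSAR.

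- **12.1.3, unexpected adverse reaction.** The test is "the nature or severity of which is not consistent with the applicable reference safety information (RSI"). A second sentence adds outcome as a ground in its own right: "When the outcome of the adverse reaction is not consistent with the applicable RSI, this adverse reaction should be considered unexpected".
- **12.1.5, SUSAR.** The whole definition is a serious adverse reaction "the nature and severity of which is not consistent with the information set out in the Reference Safety Information". Outcome is not mentioned.
- **12.1.6, RSI.** The RSI defines which reactions are expected and "thus determines which Serious Adverse Reactions (SARs) require expedited reporting".
- **12.6 and 12.6.3.1, reporting.** Suspected reactions that are "both unexpected and serious (SUSARs) are subject to expedited reporting", and the minimum criteria for an initial report again ask for an event judged serious and unexpected.

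Section 12.6.1 names the recipients of a SUSAR notification: the Sponsor, the competent authorities and the ethics committee. Sections 12.6.2.1 and 12.6.2.2 set the limits at 7 calendar days for fatal or life-threatening SUSARs and 15 calendar days for the others.

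**The concern.** A SUSAR should be a serious adverse reaction that is also unexpected, and the protocol defines both terms. The section headed SUSAR does not combine them. It restates the expectedness test with a different conjunction and without the outcome sentence. An assessor who looks up the term finds a narrower rule than the one in 12.1.3 and 12.6.

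The classification matters because it decides whether the Chief Investigator must notify the competent authority and ethics committee within the 7-day or 15-day limit. Under 12.5, SAEs in general are neither recorded nor reported in the trial, and under section 17 the TSC is the only oversight committee. The rule that sorts SARs into expedited and non-expedited should therefore have one meaning.

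**Working it through.** No figure is involved, so the check is a logical comparison. Take a serious adverse reaction judged related to the trial drug. Let N, S and O mean that its nature, severity or outcome is inconsistent with the RSI.

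- 12.1.3: unexpected = N or S or O.
- 12.6 and 12.6.3.1: SUSAR = serious and unexpected, which for a serious reaction is N or S or O.
- 12.1.5, read literally: SUSAR = N and S.

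| Inconsistent with RSI | SUSAR by 12.1.3 with 12.6 | SUSAR by 12.1.5 | Agree? |
|---|---|---|---|
| none | no | no | yes |
| N only | yes | no | no |
| S only | yes | no | no |
| O only | yes | no | no |
| N and O | yes | no | no |
| S and O | yes | no | no |
| N and S | yes | yes | yes |
| N, S and O | yes | yes | yes |

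The rules agree in 3 of the 8 combinations and disagree in 5. These are logical cases, not event frequencies. Every disagreement runs the same way: 12.1.5 is the narrower rule.

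Two rows show that the literal wording is unlikely to be intended. In the N-only row, a serious reaction of a kind not in the RSI, but of unremarkable severity, would not be a SUSAR. In the O-only row, 12.1.3 states outright that the reaction is unexpected, while 12.1.5 has no term that could capture it.

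Section 12.5 has a default under which a SAR report without an expectedness assessment is handled as a SUSAR. That covers a missing assessment. It does not cover a completed assessment that followed 12.1.5.

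**The case against.** The strongest reply is that the operative text already carries the broader rule. Section 12.1.5 is a definition and contains no reporting instruction. The instructions are in 12.6 and 12.6.3.1, both turn on *unexpected*, and that word is defined in 12.1.3 with *or* and with the outcome sentence. A careful reader of 12.6 would expedite correctly. This stands, and it limits the consequence. It does not remove the contradiction, because the protocol does not say which section prevails.

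A second reply is grammatical. Nature and severity could be read as one combined description, so that a mismatch in either makes the whole inconsistent. That reading would bring 12.1.5 into line with 12.1.3 on nature and severity. It would still omit outcome, and a definition open to two readings needs correcting anyway.

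A third reply concerns the other channels. All SARs go to the Sponsor within 24 hours (12.5), and the TSC can review SARs as well as SUSARs (section 17). The Chief Investigator must also promptly report to the competent authority any reportable serious findings that could affect participants' health or the balance of risk and benefit (12.5), and annual safety reports go to the REC and MHRA (18.1, 18.2). Bleeding events, haemorrhage progression and mortality are collected as secondary outcomes (8.6.2). All of this stands. Events are not hidden; what may slip is the individual expedited report.

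A reader might go further and infer that a fatal bleed would escape SUSAR reporting. The documents do not support this. Whether such a bleed is unexpected depends on section 4.8 of the product characteristics for each agent class, which the protocol cites but does not reproduce. An event that "results in death" is serious under 12.1.4, but that says nothing about its expectedness. Death is also an outcome, so the example would turn on the missing outcome clause and not on the conjunction between nature and severity.

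**Conclusion.** The point holds as a minor wording defect. Section 12.1.5 is out of line with 12.1.3, 12.6 and 12.6.3.1. Read literally, it excludes serious related reactions that the reporting clauses require to be expedited, including those in which only the nature, only the severity or only the outcome departs from the RSI.

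The exposure is confined to expedited notification of the competent authority and ethics committee. It arises only if two conditions are met: an assessor classifies by the literal text of 12.1.5, and the reaction departs from the RSI in some respect but not in both nature and severity. How often that would happen cannot be computed, because the protocol gives neither the RSI text nor an expected number of SARs. It would be too strong to say that reportable events will go unreported. Sample size, power and the primary analysis are not affected.

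**What to change.** Reconcile 12.1.5 with 12.1.3 and 12.6. Either of two edits does it:

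1. Define a SUSAR in 12.1.5 as a serious adverse reaction (as in 12.1.4) that is unexpected as defined in 12.1.3.
2. Keep the present sentence, change *and* to *or*, and add that an outcome inconsistent with the RSI also makes the reaction unexpected.

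The first is preferable because it leaves one expectedness test in the protocol, so the two sections cannot drift apart again. If the SAR reporting form or site training material repeats the 12.1.5 wording, it should be changed to match.

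The cost is one sentence in an amendment. The edit asks for no expedited report that 12.6 does not already require, and it needs no change to data collection or analysis.

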12.1.6 Reference Safety Information (RSI)

A list of medical events that define which reactions are expected for the IMP within a given trial and thus determines which Serious Adverse Reactions (SARs) require expedited reporting.

For this trial, the Reference Safety Information contains a clearly identified section 4.8 of the Summary of Product Characteristics (SmPC) for different drug classes.

12.1.7 Table for IMP class with SmPCs and text revision date for RSI/IMP class	RSI	Text revision Date
LMWH	Inhixa 4,000 IU (40 mg)/0.4 mL solution for injection	23/05/2023
Low molecular weight sulphated glycosaminoglyuronans	Danaparoid Sodium 750 anti-Xa units/0.6 ml, solution for injection	01/2021
Direct oral Anticoagulants (DOAC)	Pradaxa 150 mg hard capsules	12/04/2024
Synthetic pentasaccharide	Arixtra Fondaparinux sodium solution for injection 2.5 mg/0.5 ml	05/12/2023
Heparin	Heparin (Mucous) Injection BP 5,000 IU	28/09/2018

12.1.8 Expected Adverse Reactions/Serious Adverse Reactions (AR /SARs)

All expected Adverse Reactions are listed in the latest MHRA-approved version of the RSI. As explained in section 12.1.6. This must be used when deciding as to the expectedness of the adverse reaction. If the adverse reaction meets the criteria for seriousness, this must be reported as in section 12.5

12.1.9 Expected Adverse Events/Serious Adverse Events (AE/SAE)

Due to the nature of TBI, affected individuals can often develop surgical and medical complications. Expected systemic or surgical complications associated with TBI will not be recorded as SAEs.

12.4 Evaluation of AESI; SAR / SUSAR

The Sponsor expects that adverse events are recorded from the point of Informed Consent regardless of whether a participant has yet received a medicinal product. The investigator should evaluate individual adverse events. This includes the evaluation of its seriousness and any relationship between the investigational medicinal product(s) and/or concomitant therapy and the adverse event (causality).

12.4.1 Assessment of seriousness

Seriousness is assessed against the criteria in section 12.1.4. This defines whether the event is an adverse event, a serious adverse event or a serious adverse reaction.

12.4.2 Assessment of causality

Definitely	A causal relationship is clinically/biologically certain. This is therefore an Adverse Reaction
Probably	A causal relationship is clinically / biologically highly plausible and there is a plausible time sequence between onset of the AE and administration of the investigational medicinal product and there is a reasonable response on withdrawal. This is therefore an Adverse Reaction
Possible	A causal relationship is clinically / biologically plausible and there is a plausible time sequence between onset of the AE and administration of the investigational medicinal product. This is therefore an Adverse Reaction
Unlikely	A causal relation is improbable and another documented cause of the AE is most plausible. This is therefore an Adverse Event
Unrelated	A causal relationship can be definitely excluded, and another documented cause of the AE is most plausible. This is therefore an Adverse Event

- Unlikely and Unrelated casualties are considered NOT to be trial drug-related
- Definitely, Probably and Possible casualties are considered to be trial drug-related

A pre-existing condition must not be recorded as an AE or an SAE unless the condition worsens during the trial and meets the criteria for reporting or recording in the appropriate section of the CRF.

12.4.3 Clinical assessment of severity

Mild	The participant is aware of the event or symptom, but the event or symptom is easily tolerated
Moderate	The participant experiences sufficient discomfort to interfere with or reduce his or her usual level of activity
Severe	Significant impairment of functioning; the subject is unable to carry out usual activities and / or the participant's life is at risk from the event

12.4.4 Recording of adverse events and Adverse Events of Special Interest

Selected AEs and ARs will be recorded and reported as part of the trial. Adverse events and adverse reactions should be recorded in the patient's medical notes as part of their routine care, as determined by their treating clinician.

Adverse Events of Special Interest (AESIs) will be recorded in the trial as part of secondary outcome data collection in the AESI eCRF. AESI that will be collected in the trial include those below:

- Thrombocytopenia
- Thrombocytosis
- Prosthetic cardiac valve thrombosis
- Cutaneous vasculitis
- Eosinophilia
- Skin reactions
- Angioedema
- Priapism
- Stevens-Johnson syndrome
- Acute generalised exanthematous pustulosis (AGEP)

12.5 Recording and reporting serious adverse events (SAEs) and serious adverse reactions (SARs)

SAEs will not be recorded or reported as part of the trial. Only SAEs for secondary outcome data (ie AESI) will be recorded in the SAE CRF for the duration of the trial.

SAEs should be recorded in the patients normal medical record as part of their routine care as determined by their treating clinician. All SAEs must be assessed by the PI or delegate for causality/relatedness to determine if the event meets the criteria for reporting to the CI and Sponsor as a Serious Adverse Reaction (SAR). See below for SAR reporting requirements.

Only SARS and SUSARs must be reported to the Chief Investigator using the trial-specific SAR reporting form within 24 hours of their event awareness. The Chief Investigator is responsible for ensuring the assessment of all SAEs for expectedness and relatedness is completed and the onward notification of all SARs and SUSARs to the Sponsor immediately but not more than 24 hours after the first notification. The sponsor must keep detailed records of all SARs reported to them by the trial team.

The Chief Investigator is also responsible for prompt reporting of all reportable serious adverse event findings to the competent authority (e.g. MHRA) of each concerned Member State if they could:

- adversely affect the health of participants
- impact on the conduct of the trial
- alter the risk-to-benefit ratio of the trial
- alter the competent authority's authorisation to continue the trial in accordance with Directive 2001/20/EC

For this trial, only Adverse Reactions that are serious (SARs) or unexpected (SUSARS) will require expedited reporting to the Sponsor.

Principal investigators must record and report SARs and SUSARs to the Sponsor within 24 hours of becoming aware of the event using the SAR form provided.

SARs/SUSARs will only be collected and reported during trial treatment

Any/all SAR reports which do not contain the expectedness assessment will be automatically considered as a SUSAR, and be subject to expedited reporting until such time as an expectedness assessment is documented and reported to the CI & Sponsor. Please see section 12.1.6 for the Reference Safety Information to be used in this trial

The completed SAR Reporting form will be emailed to the coordination centre. Details of where to report the SARs can be found on the TOP-TBI SAR Reporting form and the front cover of the protocol.

12.6 Reporting of Suspected Unexpected Serious Adverse Reactions (SUSARs)

All suspected adverse reactions related to an investigational medicinal product (the tested IMP and comparators) which occur in the concerned trial and that are both unexpected and serious (SUSARs) are subject to expedited reporting. Please see section 4.8 for the Reference Safety Information for this trial.

12.6.1 Who should report and whom to report to?

The Sponsor delegates the responsibility of notification of SUSARs to the Chief Investigator. The Chief Investigator must report all the relevant safety information previously described to the:

- Sponsor
- Competent authorities in the concerned member states (e.g., MHRA)
- Ethics Committee in the concerned member states

The Chief Investigator shall inform all investigators concerned of relevant information about SUSARs that could adversely affect the safety of participants.

12.6.2 When to report?

12.6.2.1 Fatal or life-threatening SUSARs

All parties listed in 12.6.1 must be notified as soon as possible but no later than 7 calendar days after the trial team and Sponsor have first knowledge of the minimum criteria for expedited reporting. In each case, relevant follow-up information should be sought, and a report completed as soon as possible. It should be communicated to all parties within an additional 8 calendar days.

12.6.2.2 Non-fatal and non-life-threatening SUSARs

All other SUSARs and safety issues must be reported to all parties listed in 12.6.1 as soon as possible but no later than 15 calendar days after first knowing the minimum criteria for expedited reporting. Further relevant follow-up information should be given as soon as possible.

12.6.3 How to report?

12.6.3.1 Minimum criteria for initial expedited reporting of SUSARs

Information on the final description and evaluation of an adverse reaction report may not be available within the required time frames for reporting. For regulatory purposes, initial expedited reports should be submitted within the time limits as soon as the minimum following criteria are met:

- a suspected investigational medicinal product
- an identifiable participant (e.g. trial participant code number)

- c) an adverse event assessed as serious and unexpected and for which there is a reasonable suspected causal relationship
- d) an identifiable reporting source

and, when available and applicable:

- a unique clinical trial identification (ISRCTN number or in the case of non-European Community trials, the sponsor's trial protocol code number)
- a unique case identification (i.e. sponsor's case identification number)

12.6.3.2 Follow-up reports of SUSARs

In case of incomplete information at the time of initial reporting, all the appropriate information for an adequate causality analysis should be actively sought from the reporter or other available sources. Further available relevant information should be reported as follow-up reports.

In certain cases, it may be appropriate to conduct a follow-up of the long-term outcome of a particular reaction.

